Immediate. Based upon prior RCT outside of the United States, the use of silicone ureteral stents has the potential to decrease pain and LUTS after URS.(12) Decreased pain and LUTS after URS secondarily could decrease the rate of ambulatory healthcare utilization, opioid prescriptions, postoperative ED visits, and unplanned hospitalizations. It could also decrease the number of days required to miss work due to recovery.

Long-range. Decreased pain and LUTS after URS secondarily could decrease a patient's exposure to opioid analgesia postoperatively. Less patient requirements for opioid analgesia could decrease the incidence of new persistent long-term use of opiates in these patients.

Section 5: STUDY OBJECTIVES**Section 5.1: Primary Objectives**

1. To determine the health-related quality of life and symptoms in patients with urinary stone disease stented with silicone or polyurethane stents at ureteroscopy.

Section 5.2: Secondary Objectives

1. To compare 30-day emergency department visits and hospitalization rates between study arms
2. To compare rates and intensity of ambulatory healthcare encounters after ureteroscopy and stenting between study arms
3. To compare stone-free rates between study arms
4. To compare abnormal imaging findings after ureteroscopy and stenting between study arms

Section 5.3: Exploratory Objectives

1. To compare days taken off work by patient between study arms
2. To compare days taken off work by caregiver between study arms
3. To compare Ecological Momentary Assessments (EMA) measured via daily text message for 10 days between study arms
4. To compare Composite score difference between Winratio and Desirability Of Outcome Ranking (DOOR) between study arms
5. To compare number of patients receiving opioid prescriptions between study arms
6. To compare ICIQ-s score at 7 days between study arms
7. To compare ICIQ-s score at 4 weeks between study arms

Section 5.4: Endpoints

- Primary Efficacy Endpoint(s):
 - Silicone stent placement will be associated with significantly improved PROMIS® scores of pain intensity and interference at 7 days compared to non-silicone stent placement.
- Secondary Efficacy Endpoint(s):
 - Silicone stent placement will be associated with equivalent PROMIS® scores of pain intensity and interference at 4 weeks compared to non-silicone stent placement.

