 - Silicone stent placement will be associated with significantly improved NIH LURN SI-10 scores from baseline at 7 days compared to non-silicone stent placement.

- Silicone stent placement will be associated with equivalent difference in NIH LURN SI-10 scores from baseline at 4 weeks compared to non-silicone stent placement.
- Silicone stent placement will be associated with improved composite healthcare utilization metric within 30 days compared to non-silicone stent placement.
 - Hospitalization and ICU care
 - Unplanned hospitalization
 - Emergency department visit
 - Ambulatory encounter: Clinic visit
 - Ambulatory encounter: Phone call or EMR message
- Silicone stent placement will be associated with equivalent abnormal imaging findings within 60 days compared to non-silicone stent placement.
 - New/worsening hydronephrosis
- Silicone stent placement will be associated with equivalent stone-free rates within 60 days compared to non-silicone stent placement.
- Tertiary/Exploratory Endpoint(s):
 - Silicone stent placement will be associated with significantly improved Ecological Momentary Assessment (EMA) scores measured via daily text message for 10 days compared to non-silicone stent placement.
 - Daily visual analog scale survey for pain
 - PROMIS® daily ability to participate in social roles and activities score
 - Silicone stent placement will be associated with significantly less number of days taken off work by patient.
 - Silicone stent placement will be associated with significantly less number of days taken off work by caregiver.
 - Silicone stent placement will be associated with significantly improved composite healthcare utilization metric within 30 days compared to non-silicone stent placement using Desirability of Outcome Rating (DOOR) method
 - The WinRatio and DOOR composite healthcare utilization metric ratios' sizes and directions will be compared.
 - Silicone stent placement will be associated with significantly less number of opioid prescriptions received.
 - Silicone stent placement will be associated with significantly improved ICIQ-S scores at 7 days compared to non-silicone stent placement.
 - Silicone stent placement will be associated with significantly improved ICIQ-S scores at 4 weeks compared to non-silicone stent placement.

Section 6: PATIENT ELIGIBILITY

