The Michigan Urological Surgery Improvement Collaborative (MUSIC) is a Michigan-based, physician-lead quality collaborative comprised of a consortium of urology practices. The collaborative is designed to evaluate and significantly improve the quality and cost efficiency of urologic care in the state of Michigan. The participating sites submit data to the MUSIC clinical registry maintained by the MUSIC Coordinating Center and attend tri-annual consortium-wide meetings each year to compare performance, share best practices, and ultimately implement changes in clinical behavior. The consortium is funded by Blue Cross Blue Shield of Michigan (BCBSM) and the program activities are managed by the MUSIC Coordinating Center, which is housed at the University of Michigan.

ROCKS is a QI initiative within MUSIC to measure the frequency of ED visits following ureteroscopy.

Eligible BLUES patients include those that are enrolled in MUSIC ROCKS and ROCKS PRO and ≥ 18 years of age with a kidney or ureteral stone and are planned to have a ureteroscopy where stent placement is planned. Based on inclusion and exclusion criteria these patients will be identified in the clinic by MUSIC urologists at practices participating in BLUES.

Subjects must meet all of the inclusion and exclusion criteria to be enrolled to the study. Study treatment may not begin until a subject is enrolled.

Section 6.1: Inclusion Criteria

In order to be eligible to participate in this study, an individual must meet all of the following criteria:

1. Provision of signed and dated informed consent form
2. Stated willingness to comply with all study procedures and availability for the duration of the study
3. Male or female, aged ≥ 18 years
4. Planned treatment of unilateral renal and/or ureteral stones, largest stone ≤ 2.0 cm in size measured on abdominal x-ray, Ultrasound or CT scan.
 - i. Renal stone defined as only renal location of stone(s).
 - ii. Ureteral stone defined as ureteral only or ureteral and renal stone(s).
5. Planned unilateral ureteroscopy with stent placement without stent string.
6. Ability to take oral medication.
7. Ability and willingness to complete and adhere to survey questions and responses throughout study duration.

Section 6.2: Exclusion Criteria

An individual who meets any of the following criteria will be excluded from participation in this study:

1. Known planned secondary or staged procedure

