Participants at a given performance site who meet all inclusion/exclusion criteria will be randomized using Randomize.net or a similar randomization methodology as endorsed by the Michigan Institute for Clinical & Health Research (MICHR). Subjects will be randomized to either silicone or non-silicone ureteral stent placement at a 1:1 allocation ratio. Blocked, stratified randomization based upon surgeon classified stone location (renal only versus ureteral), with random block sizes will be used to ensure group balance. Randomization list will be determined separately in strata defined by state the stratification factor/s here. The randomization code will be generated by an independent statistician.

At the time of surgery, if baseline PRO has been completed, prior to placement of the stent, the surgeon will be notified via email/text message and the surgeons operating room staff can reference the MUSIC registry to confirm if the patient should have a silicone vs non-silicone stent based on random allocation by the BLUES study coordinator or another member of the BLUES study team. Only patients who are randomized, remain eligible prior to stent placement, and receive the study treatment will be counted towards the treatment population of 224 participants. These patients will receive PRO questionnaires, via the ROCKS PRO infrastructure, pre-operatively and at 7 days, and 4 weeks after surgery. If the patient is unable to complete the PRO questionnaires through the ROCKS PRO infrastructure, the patient may complete an email survey via REDCap, survey by phone from a BLUES study team member, or paper questionnaires. Patients will also receive text messages which include pain-specific questionnaires to be completed daily for 10 days after surgery. The process of completing the ROCKS PRO questionnaire is

the same, regardless of the patient's participation in the BLUES study. A patient can withdraw or decline participation in BLUES and/or ROCKS PRO at any time.

Section 8: TREATMENT PLAN

Section 8.1: Treatment overview

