The patient's post-operative care will proceed per standard of care, and their follow up, imaging and clinic visits will be directed by the local surgeon according to their local protocol. All patients will be provided with the MUSIC pain optimization pathway (POP) medication for post-operative symptoms for ureteroscopy. The standard within MUSIC is to prescribe non-steroidal anti-inflammatory drugs (NSAIDs), alpha-blockers and an anti-cholinergic as first line therapy. Opiate pain medication is not recommended as first line therapy. Patients will also be provided the MUSIC pain management and stent specific education brochures.

The BLUES study is pragmatic. Stents will be removed at a time and duration per the surgeon's discretion. The patient's information regarding post-operative course will be collected into the registry 60 days after the surgery, keeping with current practice for MUSIC ROCKS patient registry entry.

Specific assessments obtained on the postoperative day 1 through 10, include:

- ROCKS PRO day 7 questionnaire
 - Participants will complete their day 7 ROCKS PRO questionnaire, consisting of PROMIS® scores of pain intensity and interference, LURN SI-10 score Baseline ICIQ-S score, stent specific USSQ question and reported number of days off work (Figure 1)
- Ecological Momentary Assessment (EMA) measured via daily text message
 - Participants will complete a single visual analog scale survey for pain and one functional ability question from the PROMIS® ability to participate in social roles and activities (Figure 2)

Specific assessments obtained on the postoperative day ≤ 60, include:

- ROCKS PRO 4-week questionnaire

- Participants will complete their 4-week postoperative ROCKS PRO questionnaire, consisting of PROMIS® scores of pain intensity and interference, LURN SI-10 score Baseline ICIQ-S score, stent specific USSQ question (Figure 1)
- Stone-free rates within 60 days
 - Participants after URS are often requested to obtain renal imaging within 8 weeks. However, since this is a pragmatic study, patients are asked to receive imaging based on provider discretion, and some patients do not attend their imaging appointment, Utilizing MUSIC and ROCKS existing infrastructure. Stone free defined as no residual fragments identified on any postoperative imaging (ultrasound, abdominal X-ray, CT or any combination) within 60 days

Section 8.4: Concomitant Medications/Treatments

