Abnormal imaging and stone-free rates will each be summarized as a count with the associated proportion by treatment arm and tested with a chi-square test (or fisher's exact test if event counts are 5 or less.)

Planned Interim Analyses

An interim analysis for futility is planned after accrual of 112 patients. The study will stop early if it is found that the silicon stent arm has clinically significant worse pain intensity and worse pain interference at 7 days with worse pain defined as 5 or greater t-score points worse pain in the silicone stent arm compared to the non-silicone stent arm after adjusting for baseline. Under the alternative hypothesis for both endpoints simulations of 1000 trials estimatas the probability of stopping early is 0%. If we assume that

the silicone stent is worse than the non-silicone stent by 5 points simulation of 1000 trials estimates the probability of stopping early is 24.4%.

Sub-Group Analyses

A sub-group analysis by stone location is planned. Primary and secondary endpoints will be reported for ureteral stones separately from renal stones.

Exploratory Analyses.

The mean (with standard deviation) or median (with interquartile range) days taken off work by patient and separately by caregiver will be compared between treatment arms with a t-test or Wilcoxon rank test if the distribution warrants.

Ecological Momentary Assessments of pain and PROMIS® daily ability to participate in social roles and activities score measured via daily text message will be displayed using spaghetti plots. Each measure will be analyzed with a linear mixed model including fixed effects of treatment arm, day, and the interaction of treatment arm and day. As this is an exploratory endpoint, these models will be explored using several methods to address missing data and model fit.

Each healthcare utilization metric within 30 days of URS will be summarized separately as a count with the associated proportion by treatment arm and tested with a chi-square test (or Fisher's exact test if event counts are 5 or less.)

In an exploratory analysis to create a composite endpoint to be used in future trials we will assess the plausibility of 2 composite measurement plans and analyses of these.

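### The 60-day stone-free comparison uses neither stone location nor baseline stone size and has no confidence interval; adjusting it would be a small, cheap improvement to a secondary endpoint

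*Combined protocol and SAP*

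**What the plan says.** - **Hypothesis (Section 5.4):** "Silicone stent placement will be associated with equivalent stone-free rates within 60 days compared to non-silicone stent placement". The matching objective in Section 5.2 is only "To compare stone-free rates between study arms". Neither gives a margin.
- **Analysis (Section 11.4, secondary endpoints):** "Abnormal imaging and stone-free rates will each be summarized as a count with the associated proportion by treatment arm and tested with a chi-square test". Small event counts switch the comparison to the Fisher version. No covariate, stratification or confidence interval is named for this endpoint.
- **Outcome (Section 8.3):** "Stone free defined as no residual fragments identified on any postoperative imaging (ultrasound, abdominal X-ray, CT or any combination) within 60 days". The same section says that "patients are asked to receive imaging based on provider discretion, and some patients do not attend their imaging appointment".
- **Location (Section 7):** "Blocked, stratified randomization based upon surgeon classified stone location (renal only versus ureteral), with random block sizes".
- **Size (Section 6.1, criterion 4):** "Planned treatment of unilateral renal and/or ureteral stones, largest stone ≤ 2.0 cm in size measured on abdominal x-ray, Ultrasound or CT scan".

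Two other parts of Section 11.4 come close. The subgroup plan reports secondary endpoints separately for ureteral and renal stones. An optional multivariable model appears under the primary pain endpoints. Neither gives an adjusted overall stone-free estimate.

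**The concern.** Eligibility runs from very small stones up to 2.0 cm, in kidney or ureter. Size and location are natural predictors of residual fragments, and both are assessed before surgery. A crude comparison of proportions uses neither, so it can be less precise than the data allow.

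The second issue is balance. Only patients with postoperative imaging have an observed stone-free status. The treating surgeon directs that imaging and knows the allocation (Section 7); the blinding described in Section 10.4 covers patients. If imaging were ordered or attended differently by stone size in the two arms, the imaged groups would differ in stone burden, and a crude test would carry that straight into the arm difference. Where the stated expectation is no difference, even a few points of false shift matter to the reading.

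**Working it through.** **1. The plan's own figures.** No rate, effect or power is stated for stone-free status. The only sizing is for pain (Section 11.2): 2 × (2.2414 + 1.2816)² × 10² / 5² = 99.3 per arm by the normal formula, and 100.6 (so 101) by the exact t-test. Then 202 / 0.9 = 224.4, against the stated 224. This reproduces but says nothing about stone-free rates. All inputs below are therefore assumptions.

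**2. Precision of the crude comparison.** 95% half-width = 1.96 × √(2p(1−p)/n), with n imaged patients per arm.
- All 112 per arm imaged, p = 0.70: 12.0 points.
- 30% without imaging (78 per arm), p = 0.70: 14.4 points.
- 80 per arm, p = 0.65: 1.96 × √(2 × 0.65 × 0.35 / 80) = 14.8 points.

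**3. Gain from adjustment.** Simulated trials with 160 imaged patients, size mean about 9.6 mm and SD about 3.8 mm, location effect 0.6 on the log-odds scale, and allocation balanced by location. The comparison is the crude risk difference against the risk difference standardised from a logistic model on arm, location and size. The half-width column is 14.8 × √(variance ratio).

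| Fall in log-odds per mm | Odds ratio per cm | Variance ratio, 65% stone-free at mean size | Half-width (points) | Variance ratio, 85% stone-free |
|---|---|---|---|---|
| 0.05 | exp(−0.5) = 0.61 | 1.00 | 14.8 | 1.01 |
| 0.10 | exp(−1.0) = 0.37 | 0.97 | 14.6 | 0.99 |
| 0.15 | exp(−1.5) = 0.22 | 0.95 | 14.4 | 0.97 |
| 0.25 | exp(−2.5) = 0.08 | 0.85 | 13.6 | 0.90 |

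The variance falls by about 0 to 15%, and the half-width by 0 to 1.2 points. Adjusting for location alone gains under 1%, because stratified randomisation already balances it. Adding an assumed measurement error of SD 3 mm to size cuts the 15% to 7%.

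**4. Shift if imaging depends on size in one arm only.** Approximately: shift = slope × p(1−p) × difference in mean size among imaged patients. An imaging log-odds gradient of 0.1 to 0.2 per mm in one arm gives a mean size difference of about 0.4 to 0.7 mm.
- Low end: 0.10 × 0.65 × 0.35 × 0.4 = 0.009, or 0.9 points.
- High end: 0.25 × 0.65 × 0.35 × 0.7 = 0.040, or 4.0 points.

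Simulation under these settings, with no true arm effect, gave crude shifts of about 0.9 to 3.6 points. The adjusted estimate stayed within 0.3 points of zero.

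**5. Does adjustment reach equivalence?** Two one-sided tests at 5%, 112 per arm, 70% stone-free, true difference zero.
- Assumed 10-point margin: power about 0% crude, 6% with a 10% variance reduction.
- Assumed 15-point margin: 58% crude, 65% with the same reduction.

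The planned chi-square test has about 35% power against a true drop from 70% to 60%, so a non-significant result would be likely even with that deficit.

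**The case against.** The strongest reply is that a crude chi-square test is valid in a randomised comparison, so covariates here are a matter of efficiency. The gain is small on the reader's scale and rests wholly on assumed inputs. The top row of gain needs the odds of being stone-free to fall about twelvefold per cm (exp(2.5) = 12.2), with size measured without error, although criterion 4 allows x-ray, ultrasound or CT and concerns only the largest stone. The comparison with the pain models is also uneven: those adjust for the same measure at baseline, and stone-free status has no baseline counterpart. All of this stands, and it limits the point to a minor one.

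It does not remove the point. Validity under randomisation applies to all randomised patients, not to a subset chosen by discretionary imaging. Subgroup reporting by location splits the sample and is not an adjusted overall estimate.

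Four stronger readings are tempting, and the documents do not support them:
- **That substantial precision is lost.** The steepest row could be read as 18% more patients (1/0.85 = 1.18), but no document figure supports a slope of that size.
- **That imaging does differ by arm.** The documents show only that it is discretionary and incomplete. The shift in step 4 is conditional on a pattern that nobody has shown.
- **That adjustment would secure the equivalence claim.** No margin is stated, and step 5 shows that covariates barely change the position.
- **That size is certainly available as an analysis variable.** Criterion 4 and the baseline imaging row in Section 9 imply it. No section says that a value in mm is stored.

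**Conclusion.** The point holds as a minor improvement to a secondary endpoint; the primary pain conclusion is unaffected. Section 11.4 leaves out the trial's own randomisation factor and a preoperative size measurement, and gives no interval for the stone-free difference. With about 160 imaged patients and an assumed fall of 0.05 to 0.25 in log-odds per mm, adjustment is worth 0 to 15% of the variance, or roughly 0 to 1 point of half-width, and nearly all of that comes from size. Its larger use is as protection: if imaging depended on size differently by arm, it would remove a shift of about 1 to 4 points. It would not correct selection driven by postoperative symptoms, surgeon choice or anything else outside the model.

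**What to change.** In Section 11.4, analyse stone-free status with a logistic model on arm, stone location and baseline largest-stone size (continuous, in mm). First confirm that the registry holds the size value; if it does not, use location only and expect almost no gain in precision. Report the standardised (marginal) risk difference with its 95% CI. The gain appears on that scale; the standard error of a conditional odds ratio would not shrink. Keep the chi-square or Fisher test as supporting.

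Two matters need their own wording, because the model does not settle them: state how patients without imaging within 60 days are handled, and either justify a margin or stop describing the expected result as equivalent.

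The cost is a change to the analysis text, one extra model and a check of one registry field. If the field is populated, no new data are needed.

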Endpoints:	
Primary Endpoint:
 
 • PROMIS® scores of pain intensity and pain interference at 7 days 
Secondary Endpoints:
 
 • PROMIS® scores of pain intensity and interference at 4 weeks • NIH LURN SI-10 scores at 7 days • NIH LURN SI-10 scores at 4 weeks • Composite healthcare utilization metric within 30 days 
 ◦ Hospitalization and ICU care ◦ Unplanned hospitalization ◦ Emergency department visit ◦ Ambulatory encounter: Clinic visit ◦ Ambulatory encounter: Phone call or message • Abnormal imaging findings within 60 days • Stone-free rates within 60 days 
Exploratory Endpoints:
 
 • Number of days taken off work by patient • Number of days taken off work by caregiver • Ecological Momentary Assessments (EMA) measured via daily text message for 10 days 
 ◦ Daily visual analog scale pain survey score ◦ PROMIS® daily ability to participate in social roles and activities score • Composite score difference between Winratio and Desirability Of Outcome Ranking (DOOR) • Number of patients receiving opioid prescriptions • ICIQ-S Treatment Satisfaction scores at 7 days • ICIQ-S Treatment Satisfaction scores at 4 weeks
Study Population:	224 patients, any gender, age ≥18 years, in the State of Michigan
Phase:	Not applicable
Description of Sites/Facilities	Multi-center study of 6 urology practices within the Michigan Urological Surgery Improvement Collaborative (MUSIC) with University of Michigan as the coordinating center.
Enrolling Participants:	
Description of Study Intervention:	Insertion of ureteral stent at the end of ureteroscopy for stone disease. Study arms will consist of either silicone (Coloplast Imajin Hydro) ureteral

stent vs. non-silicone (Polyurethane/Percuflex) ureteral stent (any manufacturer).
Study Duration: 30 months (3 months pre-enrollment and set up; 24 months patient enrollment; 3 months study close and analysis).
Participant Duration: 2 months

Section 3: STATEMENT OF COMPLIANCE

The study will be carried out in accordance with United States (US) Code of Federal Regulations (CFR) applicable to clinical studies (45 CFR Part 46, 21 CFR Part 50, 21 CFR Part 56, and/or 21 CFR Part 812)

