It is not anticipated that either arm will be associated with adverse events above and beyond what is experienced normally with these therapies. No more than minimal increased risk to the participants is expected for the present study. All potential participants are planning to undergo a surgical procedure (URS) with a board-certified urologist trained in URS with stent placement in accordance with AUA guidelines. They will be placing either a non-silicone (standard) ureteral stent or a silicone ureteral stent, both of which are FDA approved. All of which is considered usual care.

At the end of ureteroscopic procedure, a ureteral stent will be placed by the urologist in the standard fashion that each urologist is trained to perform. Stent sizing, technique, duration and removal technique will be determined by the individual urologist and their standard practice.

Patients randomized to the silicone stent cohort will utilize the Coloplast Imajin Hydro (Silicone Hydro-Coated Double Loop Ureteral Stent)

- This stent is commercially available and is being used in accordance with approved labeling: "The Silicone Hydro-Coated Double Loop Ureteral Stents are used for:
 - Drainage of the upper urinary tract over fistulas or ureteral obstacles
 - Healing of the ureter"
- Stent sizes
 - 6fr x 24

-
- 6fr x 26
 - 6fr x 28

Patients randomized to the non-silicone stent cohort will utilize any commercially available non-silicone ureteral stent for its approved indication. The stents denoted below are commonly used non-silicone stents and are not individually compared against the object of the study (Imajin Hydro silicone stent above).

- Device model(s)
 - Boston Scientific
 - Percuflex™
 - HYDROGEL COATED Percuflex Plus™
 - Contour™
 - Becton Dickinson (Bard)
 - Bard double pigtail soft polyurethane
 - Cook
 - Sof-Flex double loop polyurethane
- Stent size(s)
 - 6fr x 24
 - 6fr x 26
 - 6fr x 28

Specific assessments obtained on the operative day, include:

- Ureteral stent characteristics
 - The ureteral stents in the comparative effectiveness study are FDA approved commercially available devices that will be utilized by the urologists. Urologists will be trained and educated on documenting the specific size, brand and name of the ureteral stent used in the operative report. This data will be collected through the ROCKS clinical registry.

Section 8.3: Post-Operative

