An interim analysis for futility is planned after accrual of 112 patients. The study will stop early if it is found that the silicone stent arm has clinically significant worse pain intensity and worse pain interference at 7 days with worse pain defined as 5 or greater t-score points worse pain in the silicone stent arm compared to the non-silicone stent arm after adjusting for baseline. Under the alternative hypothesis for both endpoints simulations of 1000 trials estimates the probability of stopping early is 0%. If we assume that the silicone stent is worse than the non-silicone stent by 5 points simulation of 1000 trials estimates the probability of stopping early is 24.4%.

Section 11: STATISTICAL CONSIDERATIONS

Section 11.1: Statistical Hypotheses

This is a multi-center two-arm stratified, randomized comparative effectiveness study in patients are treated with URS for nephrolithiasis with a planned placement of a stent to assess patient reported quality of life. The primary hypothesis is that the silicone ureteral stent arm will have superior patient reported pain outcomes compared to the non-silicone stent arm. Patients will be stratified by stone location (kidney only / ureteral) and randomized to receive a silicone stent or a non-silicone stent and complete the PROMIS® pain intensity and PROMIS® pain interference surveys prior to surgery and at 7 days after stent placement.

Our formal statistical hypotheses are:

$$H_0: \mu_{ns} = \mu_{ss}, \quad H_1: \mu_{ns} \neq \mu_{ss}$$

where, μ_{ns} = mean PROMIS® pain intensity in non-silicone stent arm at 7 days

μ_{ss} = mean PROMIS® pain intensity in silicone stent arm at 7 days

AND

$$H_0: w_{ns} = w_{ss} \quad H_1: w_{ns} \neq w_{ss}$$

where, w_{ns} = mean PROMIS® pain interference in non-silicone stent arm at 7 days

w_{ss} = mean PROMIS® pain interference in silicone stent arm at 7 days

Section 11.2: Power/Sample Size:

Assume that the correlation of baseline is 0 for purposes of the sample size calculation. If this assumption is violated, the power for each hypothesis will be greater than the stated power.

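### Control stent, dwell time and removal technique follow each urologist's practice, but practice is in neither the randomisation strata nor the primary ANCOVAs, which costs a little precision and is cheap to fix

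*Combined protocol and SAP*

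**What the plan says.** **Randomisation.** Section 7: "Subjects will be randomized to either silicone or non-silicone ureteral stent placement at a 1:1 allocation ratio". The method is: "Blocked, stratified randomization based upon surgeon classified stone location (renal only versus ureteral), with random block sizes will be used to ensure group balance". Section 11.1 agrees on the factor: "Patients will be stratified by stone location (kidney only / ureteral) and randomized to receive a silicone stent or a non-silicone stent". The Section 7 sentence that should list the strata is unfilled template text: "Randomization list will be determined separately in strata defined by state the stratification factor/s here". Neither practice nor surgeon is named as a factor.

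**Sites.** The synopsis (Section 2) describes a "Multi-center study of 6 urology practices within the Michigan Urological Surgery Improvement Collaborative (MUSIC").

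**What varies locally.** The silicone arm uses one named product. For controls, Section 8.2 says: "Patients randomized to the non-silicone stent cohort will utilize any commercially available non-silicone ureteral stent for its approved indication". It also says: "Stent sizing, technique, duration and removal technique will be determined by the individual urologist and their standard practice".

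**What is common to all practices.** Section 6.1 requires a planned stent without a string. Section 8.3 provides the MUSIC pain pathway medication to all patients, with a stated first-line standard. Section 8.4 asks participants to follow their treating surgeon and describes the MUSIC guidance as recommended.

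**Analysis.** Section 11.4 models each day-7 PROMIS T-score on arm and baseline score. A further multivariable model is to be considered for variables that turn out unbalanced. It names stent-removal timing and stone location, not practice.

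**Comparator wording.** Section 5.1 states the objective as: "To determine the health-related quality of life and symptoms in patients with urinary stone disease stented with silicone or polyurethane stents at ureteroscopy". The synopsis objective, Section 5.4, Section 8.2 and the Section 11.1 hypotheses all refer to non-silicone stents.

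**The concern.** Practice is a plausible carrier of differences in day-7 pain. Section 4.3 says stents are often removed 1 to 3 weeks after placement, and the primary questionnaire is accepted on days 7 to 10. A practice's removal habit may therefore decide whether the stent is still in place at assessment. The control product can differ by practice too.

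Practice is known before randomisation, so it could be balanced by design and adjusted for without difficulty. The plan does neither. Two things follow. The arms can draw unequally on individual practices by chance, and between-practice variation inflates the residual variance of the primary models. At stake are the precision of the two primary comparisons and how easily a reader can discount practice as an explanation for the observed difference.

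**Working it through.** **Inputs from the documents.** Difference 5 T-score points, SD 10, two-sided alpha 0.025 per endpoint, 101 analysed per arm, 90% power, 224 accrued (all Section 11.2); six practices (Section 2); 1:1 allocation (Section 7).

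**Assumptions.** The documents give no between-practice share of variance (ICC, written ρ), practice sizes or block sizes. I take ρ = 0.02, 0.05 and 0.10.

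**1. The plan's own figure.** A two-sample t-test with standardised difference 5/10 = 0.5 and alpha 0.025 needs 100.6, so 101, per arm; power at 101 is 0.901. The stated figure is reproduced.

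**2. How often practices split unevenly.** Six equal practices have 224/6 ≈ 37 patients each. If allocation within a practice behaves like Binomial(37, 0.5):

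| Split or worse | One given practice | At least one of six |
|---|---|---|
| 23:14 | 2·P(X ≤ 14) = 0.188 | 1 − (1 − 0.188)^6 = 0.71 |
| 24:13 | 2·P(X ≤ 13) = 0.099 | 1 − (1 − 0.099)^6 = 0.46 |

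A simulation of 4,000 trials used 202 analysed patients and blocks of 2, 4 and 6 stratified on stone location only. It found at least one practice split 60:40 or worse in 76% of trials with equal practices, and in 89% with sizes of 40/20/15/10/10/5%. Uneven splits are the normal case.

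**3. What an uneven split does to the result.** Suppose a practice splits 23:14 and its patients average a full 5 points worse than all others. The arm difference then moves by 5 × (23 − 14)/112 = 0.4 points. Over all practices, the chance contribution has SD 10·√ρ·√(2/101):

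| ρ | SD of shift | 95% range (±1.96 SD) |
|---|---|---|
| 0.02 | 0.20 | ±0.39 |
| 0.05 | 0.31 | ±0.62 |
| 0.10 | 0.44 | ±0.87 |

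These compare with a 5-point target and an SE of 1.41. In the simulation (ρ of 0.05 and 0.10), type I error without practice in the model was 0.025 to 0.028 against a nominal 0.025.

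**4. What adjustment gains.** With total SD 10, removing the between-practice share gives SE = 10·√(2(1 − ρ)/101); power is from the t-test at 101 per arm:

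| ρ | SE | Power |
|---|---|---|
| 0 (no gain) | 1.41 | 0.901 |
| 0.02 | 1.39 | 0.907 |
| 0.05 | 1.37 | 0.916 |
| 0.10 | 1.33 | 0.931 |

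**5. Sensitivity to the meaning of SD 10.** If 10 is the within-practice SD, the total SD is 10/√(1 − ρ). Power without adjustment (normal approximation, 0.905 at ρ = 0) is then 0.899, 0.889 or 0.871 at ρ = 0.02, 0.05 or 0.10.

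**The case against.** **Chance imbalance is already covered.** The test and confidence interval allow for it. The high probability of an uneven split in some practice is not an effect on the result. This stands, and it rules out a reading that a reader might draw: that omitting practice biases the primary comparison or raises its error rate. Steps 3 and 4 show a small loss of precision and nothing more.

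**Local care is the pragmatic design, and it is not wholly open.** This also stands. All patients are provided the pain pathway medication and strings are ruled out at planning, so it would be wrong to say that analgesia and removal are simply left to each practice. Some prescribing discretion remains under Section 8.4. Comparator brand exists in one arm only, so it cannot be imbalanced between arms; practice mix changes only what silicone is compared with.

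**The multivariable model already covers dwell time.** This stands in part. The model is optional and does not name practice. Removal timing is decided after allocation, so adjusting for it is supportive only and does not replace adjustment for a baseline factor.

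**Pooled blocks are an inference.** This is fair: the sentence defining the lists is a placeholder. Stone location is nevertheless the only factor named in both Section 7 and Section 11.1.

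**Stratifying by practice has a price.** Small blocks within a practice make the next allocation easier to guess, because surgeons see the assignments. This stands and is counted under the fix.

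**Conclusion.** The point holds as a cheap improvement in precision. At an assumed practice ICC of 2%, 5% or 10%, adjustment would lower the SE from 1.41 to 1.39, 1.37 or 1.33 and raise power from about 90% to 91%, 92% or 93%. These figures assume that SD 10 is the total SD and that 101 patients per arm are analysed. The planned 224 need not change.

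A reader might also infer from Section 5.1 that the stated objective cannot be answered, because controls may receive stents other than polyurethane. The documents do not support that. The synopsis, endpoints, hypotheses and Section 8.2 all define the comparator as non-silicone, so the question is clear and one word in Section 5.1 is out of line.

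Nor is a randomised comparison with polyurethane necessarily lost. Practice and surgeon are fixed before allocation and stent brand is recorded, so the patients of a surgeon whose controls all receive polyurethane would form a randomised subset.

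Practice adjustment has a limit. Section 10.4 provides for blinding of patients only. Dwell time and prescribing are decided after allocation by surgeons who know the arm, so they could differ systematically between arms. Neither stratifying nor adjusting by practice addresses that.

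**What to change.** 1. **Primary model (Section 11.4).** Add practice as a fixed effect, and stone location as the existing stratification factor, to both primary ANCOVAs. Cost: 5 + 1 = 6 degrees of freedom with about 202 analysed patients, which is negligible.

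2. **Randomisation (Section 7).** Replace the template sentence with the actual strata. If recruitment has not started, add practice: 6 × 2 = 12 strata averaging 224/12 ≈ 19 patients, with random block sizes. Cost: one randomisation-system setting, and somewhat easier guessing of the next allocation within a practice. If recruitment is under way, the change to the model alone still recovers most of what is available, provided it is fixed before any unblinded analysis.

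3. **Wording.** Align Section 5.1 with the non-silicone comparator used elsewhere. Reconcile Sections 8.3 and 8.4 on the standing of the pain pathway.

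4. **Reporting.** Tabulate stent brand, dwell time, whether the stent was in place at day 7, and analgesic use by arm and practice.

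5. **Optional.** Have the surgeon record, before the arm is revealed, the non-silicone stent they would use. This allows a supportive comparison among patients with a pre-declared polyurethane stent. It would be underpowered: if half the patients qualify (an assumption, about 50 per arm), power for 5 points at alpha 0.025 is about 59%.
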